## 4. Study Objectives

Table JAIM.4.1 provides the protocol defined primary and major secondary objectives and endpoints of the study.

The estimand (EMA 2020) associated with each endpoint/analysis is documented in the following places:

- The population of interest is described in the protocol inclusion/exclusion criteria and in this document in Table JAIM.6.2 and Section 6.2.
- The endpoints/variables may be found in Table JAIM.6.3 and Table JAIM.6.4.
- The handling of intercurrent events and missing data may be found in Section 6.4.2.
- Population summary measures are described in Table JAIM.6.4.

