## 6. A Priori Statistical Methods

### 6.1. General Considerations

This Statistical Analysis Plan (SAP) describes analyses that will be utilized for the full clinical study report (CSR) for Study JAIM, at the time of JAIM primary outcome database lock. Analyses to be produced prior to the JAIM primary outcome database lock, for purposes of regulatory submissions, will be identified in the retained list of analyses. Additional safety analyses that integrate data from the originating studies will be specified in the integrated safety analysis plan (ISAP) for SLE. Any exploratory analyses will be described in a separate document. Statistical analysis of this study will be the responsibility of Eli Lilly and Company or its designee.

Not all displays described in this SAP will necessarily be included in the CSR. Not all displays will necessarily be created as a “static” display. Some may be incorporated into interactive display tools such as Spotfire instead of, or in addition to, a static display. Any display described in this SAP and not included in the CSR would be available upon request.

Throughout this document, references to analyses of corticosteroids refer to analyses of systemic corticosteroids, unless otherwise specified.

Statistical analyses of categorical safety and efficacy endpoints will be descriptive in nature.

Frequency counts and percentages by treatment arm (see [Table JAIM.6.1](#)) will be provided for the safety and efficacy endpoints. For non-model-based efficacy endpoints, 95% confidence intervals (CIs) for single proportions using the Wilson Score (Wilson, 1927; Newcombe, 1998) method will be utilized.

Unless otherwise stated, inferential statistical analyses (p-values and 95% CIs) which compare treatment groups will not be conducted.

For continuous efficacy and health outcomes endpoints the significance of within-treatment group changes from baseline will be evaluated by testing whether the treatment group least squares mean (LS mean) changes from baseline are different from zero; the 95% CI and the standard error for the LS mean change will also be displayed.

Change from baseline (defined in [Section 6.3](#)) will be calculated as the postbaseline (at that visit) value minus the baseline value. If all baseline values are missing for a particular variable, the change from baseline and percent change from baseline will not be calculated.

[Table JAIM.6.1](#) summarizes the treatment arms based on the treatment assigned in JAIM.

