## 6.4. Analysis Methods

Continuous efficacy and health outcome variables, except for Systemic Lupus International Collaborating Clinics (SLICC)/American College of Rheumatology (ACR) Damage Index will use a restricted maximum likelihood-based mixed model for repeated measures (MMRM) analysis. The response variable will be change from baseline across postbaseline visits. The model will include the following explanatory variables as fixed factors: treatment, baseline disease activity (total SLEDAI-2K  $<10$ ;  $\geq 10$ ), baseline corticosteroid dose ( $<10$  mg/day;  $\geq 10$  mg/day prednisone or equivalent), region (North America, Central/South America/Mexico, Europe, Asia and Rest of World), visit (as categorical variable), baseline value, treatment-by-visit interaction, and baseline value-by-visit interaction. Within-patient variance-covariance errors will be modeled using an unstructured covariance matrix. If this analysis fails to converge, the following structures will be tested in this pre-specified order: 1) heterogeneous Toeplitz (TOEPH), 2) heterogeneous autoregressive (ARH[1]), 3) heterogeneous compound symmetry (CSH), and 4) autoregressive (AR[1]). The Kenward-Roger method will be used to estimate the degrees of freedom. For each treatment group the least squares mean (LS mean), standard error, within-treatment p-value, and 95% CIs will be reported.

Systemic Lupus International Collaborating Clinics (SLICC)/ACR Damage Index change from baseline will be summarized with observed and modified last observation carried forward (mLOCF).

The binary efficacy measures will be summarized with observed case and non-responder imputation (NRI).

For both efficacy and safety evaluations, if study drug is temporarily interrupted (suspended) during a treatment period, the measurements taken during the temporary interruption will be included in the analysis.

Both observed and imputed analyses will be performed for efficacy and health outcomes measures.

All analyses will include the treatment arms given in [Table JAIM.6.1](#).

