### **6.4.2. Handling of Dropouts or Missing Data**

Due to the long duration of JAIME, missing data that are imputed will be carried forward for the visit interval at Week 48, Week 108, and Week 156. Discontinued patients will not be included for evaluation in intervals subsequent to their discontinuation from the study. The following visit intervals are defined for NRI method and mLOCF method:

- Visit 6 (Week 48) [ $>$  Visit 1 (Week 0) and  $\leq$  Visit 6 (Week 48)]
- Visit 9 (Week 108) [ $>$  Visit 6 (Week 48) and  $\leq$  Visit 9 (Week 108)]
- Visit 11 (Week 156) [ $>$  Visit 9 (Week 108)]

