#### **6.4.2.1. As-Observed Analysis**

The “as-observed” strategy is used in so-called “observed cases” or “completers” analysis, ubiquitous in the literature, but is not one of the recommended strategies in the ICH E9(R1). For this analysis, only data from completers at the visit are relevant, and therefore the analysis does not need to deal with missing data. This estimand is based on the subset of patients who would complete treatment through Visit X if assigned to it. Therefore, this estimand is conditional and targets the effect of treatment conditional on completion of treatment through the time point of interest. Because the estimand is defined for a subpopulation conditional on an intercurrent event, it is not causal. Summaries based on observed data at each postbaseline visit will be provided.

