#### **6.4.2.2. Non-responder Imputation (NRI)**

The NRI method may be used when the estimand of interest uses the composite strategy (EMA 2020) for handling intercurrent events. In this strategy, patients with any intercurrent event that leads to the permanent discontinuation of assigned study treatment or to prohibited medication use are defined to have failed treatment for that particular visit interval but not for the subsequent visit intervals (as defined in Section 6.4.2). Therefore, using a composite estimand approach, no data would be missing and the function of the NRI is to estimate the estimand.

All patients who discontinue the study or permanently discontinue study treatment at any time for any reason or patients who have a prohibited medication in a particular visit interval will be defined as non-responders for that visit interval and excluded from the subsequent visit intervals. Enrolled patients without at least one postbaseline observation will be defined as non-responders for the first visit interval (Visit 6) and excluded from evaluation in subsequent visit intervals.

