**Table JAIM.6.4. Description of Efficacy/Health Outcomes Analyses**

Measure	Variable	Analysis Method	Population	Key Time Point(s) a
SRI-4	Proportion of patients achieving SRI-4 response	Descriptive analysis with observed and NRI	mITT, patients with SLEDAI-2K score of $\geq 4$ at baseline	Week 156 visit
SRI-x (where x is 5, 6, 7, 8)	Proportion of patients achieving SRI-x response	Descriptive analysis with observed and NRI	mITT, patients with SLEDAI-2K score of $\geq x$ at baseline	Week 156 visit
SLEDAI-2K	Change from baseline in mean total SLEDAI-2K through Week 156	MMRM	mITT	Week 156 visit
	Proportion of patients achieving reduction of $\geq 4$ points from baseline	Descriptive analysis with observed and NRI	mITT, patients with SLEDAI-2K score $\geq 4$ at baseline	Week 156 visit
	Proportion of patients with improvement in each SLEDAI-2K individual organ systems vs baseline	Descriptive analysis with observed and NRI	mITT, patients with SLEDAI-2K score $> 0$ within the organ domain at baseline	Week 156 visit
	Proportion of patients with worsening in each SLEDAI-2K individual organ system vs baseline	Descriptive analysis with observed and NRI	mITT, patients with at least 1 SLEDAI-2K item = 0 in the organ domain at baseline	Week 156 visit
BILAG	Proportion of patients with no new BILAG A and no more than 1 new BILAG B disease activity score (compared with baseline)	Descriptive analysis with observed and NRI	mITT	Week 156 visit
	Proportion of patients with improvement in each BILAG individual organ system vs baseline	Descriptive analysis with observed and NRI	mITT, patients with BILAG A or B in the organ domain at baseline	Week 156 visit
	Proportion of patients with worsening in each BILAG individual organ system vs baseline	Descriptive analysis with observed and NRI	mITT, patients without BILAG A in the organ domain at baseline	Week 156 visit
PGA	Proportion of patients with no worsening in PGA (compared with baseline)	Descriptive analysis with observed and NRI	mITT	Week 156 visit
	Change from baseline in PGA score over time through Week 156	MMRM	mITT	Week 156 visit
BICLA	Proportion of patients achieving BICLA response	Descriptive analysis with observed and NRI	mITT	Week 156 visit
28 Tender/Swollen Joint Count	Change from baseline in tender joint count	MMRM	mITT	Week 156 visit
	Change from baseline in swollen joint count	MMRM	mITT	Week 156 visit

Measure	Variable	Analysis Method	Population	Key Time Point(s) a

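### Week 156 NRI responder rates are labelled mITT but leave out patients who discontinued or used prohibited medication by Week 108, and no binary efficacy summary in this SAP keeps the full denominator after Week 48

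*SAP*

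**What the plan says.** SAP 6.4.2 divides follow-up into three intervals (up to Week 48, from there to Week 108, and after Week 108 to Week 156) and gives the length of the study as the reason. It adds: "Discontinued patients will not be included for evaluation in intervals subsequent to their discontinuation from the study". SAP 6.4.2.2 applies this to NRI. Patients who leave the study, permanently stop treatment or take prohibited medication "will be defined as non-responders for that visit interval and excluded from the subsequent visit intervals". Patients with no postbaseline observation count as failures in the first interval only. The section calls this a composite strategy, with failure confined to the interval of the event, and concludes: "Therefore, using a composite estimand approach, no data would be missing".

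For binary efficacy measures, SAP 6.4 offers two summaries, observed case and NRI. Of the as-observed approach, SAP 6.4.2.1 says that "this estimand is conditional and targets the effect of treatment conditional on completion of treatment through the time point of interest".

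Table JAIM.6.4 has 13 rows analysed with NRI, each with key time point Week 156. The population column says mITT, sometimes with a baseline condition; the row "Proportion of patients achieving BICLA response", for example, says only mITT. Table JAIM.6.2 defines mITT as everyone dosed in JAIM, apart from one excluded site, with no retention condition.

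SAP section 4 discloses the rule by reference: "The handling of intercurrent events and missing data may be found in Section 6.4.2". Protocol 10.3.3.1 describes NRI without an interval limit but leaves the choice of method for each analysis to the SAP.

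**The concern.** A Week 156 rate labelled mITT reads as the share of treated patients in response at three years. Under the SAP rule it is the share among those who passed Week 108 without an exit or prohibited medication. Earlier failures are not counted as failures at Week 156; they are absent.

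The removed patients are unlikely to be a random subset. Protocol 5.1 and 8.1.2 ask investigators to consider discontinuing patients with insufficient benefit. Protocol 8.1.2 also lists the need for a non-permitted SLE therapy as a reason to stop treatment permanently.

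The practical risk is in reading the time course. Equal rates at Week 48 and Week 156 would look like maintained response although the number of responders had fallen. CLASI shows this most plainly: the Schedule of Activities collects it at Week 48 and next at Week 156, so two adjacent results have different denominators.

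**Working it through.** The documents state no Week 156 rate, no Week 156 denominator and no JAIM attrition rate, so there is no plan figure to reproduce. The check traces denominators and then sizes the gap.

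**1. Denominators under SAP 6.4, 6.4.2, 6.4.2.1 and 6.4.2.2.** N is the endpoint-specific mITT, meaning mITT after any baseline condition in Table JAIM.6.4.

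| Visits | NRI denominator | Observed case |
|---|---|---|
| Weeks 4 to 48 | N | patients observed at the visit |
| Weeks 60, 84, 108 | N minus those with an event by Week 48 | patients observed at the visit |
| Weeks 132, 156 | N minus those with an event by Week 108 | patients observed at the visit |

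An event is discontinuation or prohibited-medication use; patients with no postbaseline observation are also removed after Week 48. The NRI column assumes that on-treatment patients with a missing response count as non-responders, which 6.4.2.2 does not say. If they were dropped instead, every NRI denominator would be smaller still, including Week 48.

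**2. Rows affected.** The 13 NRI rows are:
- SRI-4 and SRI-5 to -8 (2)
- SLEDAI-2K reduction, organ improvement and organ worsening (3)
- BILAG no worsening, organ improvement and organ worsening (3)
- PGA no worsening, BICLA, CLASI, LLDAS and EQ-5D-5L items (5)

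In 11 of them an exit counts as not meeting the endpoint. For the two organ-worsening rows the SAP does not say which outcome NRI assigns, so they are left out of the arithmetic.

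**3. Ratio.** Let f be the share of N removed by Week 108 and R the Week 156 responders.
- SAP rate = R / (N(1-f))
- Full-denominator rate = R / N
- Ratio = 1/(1-f): 1/0.90 = 1.11; 1/0.80 = 1.25; 1/0.70 = 1.43; 1/0.60 = 1.67

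**4. Bracketing f (assumption).** The nearest planning figure is 80% completion of the 52-week originating studies (protocol 10.1), a loss of a = 0.20 per 52 weeks. With a constant rate, f = 1-(1-a)^(108/52):

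| a per 52 weeks | f | 1/(1-f) | Reported 50% equals, on the full denominator |
|---|---|---|---|
| 0.20 | 37.1% | 1.59 | 31.5% |
| 0.10 (half) | 19.7% | 1.24 | 40.2% |
| 0.05 (a quarter) | 10.1% | 1.11 | 44.9% |

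Extension patients are selected completers, so loss may be lower; prohibited-medication use adds to it.

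**5. How the time course would look.** Take 1100 patients, a = 0.10, and a 50% response among patients still event-free (both rates assumed).
- Week 48: 1100 × 0.9^(48/52) × 0.5 = 499 responders; 499/1100 = 45.4%
- Week 156, SAP: 1100 × 0.9^3 × 0.5 = 401 responders; denominator 1100 × 0.9^(108/52) = 884; 401/884 = 45.4%
- Week 156, full denominator: 401/1100 = 36.5%

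The two SAP rates agree because the event rate and on-treatment response are held constant and the first and last intervals are both 48 weeks long.

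**The case against.** The strongest reply is that this is a disclosed design choice. SAP 6.4.2 states the rule and its reason, section 4 points to it, and protocol 10.3.3.1 leaves the method to the SAP. That stands. A reader might infer a hidden rule or a breach of the protocol, and the documents support neither.

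A reader might also take "Therefore, using a composite estimand approach, no data would be missing" as a flat contradiction. The preceding sentence in 6.4.2.2 limits failure to the interval of the event, so the claim belongs to an interval-specific composite. The wording is loose: it holds at most for patients still evaluated in that interval.

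It can be said that the population column only names the analysis set, and that the method column leads to 6.4.2.2. That is fair as a reading aid, but the column does list baseline restrictions and omits this one.

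Recoverability is a real point. SAP 6.1 plans counts and percentages by arm, and the footnote to Table JAIM.6.4 plans every visit. Week 156 responders over the Week 48 denominator can therefore largely be rebuilt. The SAP still does not present that rate as a result.

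Finally, the integrated efficacy plan and the separate exploratory and health-outcomes plans were not available and may hold a full-denominator summary. The point is confined to this SAP.

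**Conclusion.** The point holds as a labelling fault and a missing summary. Week 156 NRI rates are conditional on being free of discontinuation and prohibited medication through Week 108; Table JAIM.6.4 does not show this, and no binary efficacy summary in this SAP keeps the full denominator after Week 48. For the 11 response rows the overstatement relative to the full-denominator rate is 1/(1-f), about 1.1 to 1.6 over the assumed range of f. It rests on counting on-treatment patients with a missing response as non-responders.

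A reader might go further and argue that the planned "95% confidence intervals (CIs) for single proportions using the Wilson Score" method fails because its interval can miss the full-denominator rate. That does not follow. The interval is for the rate among patients still evaluated, a different target, so missing the other rate is not a defect of the interval.

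The consequence is bounded. Efficacy is secondary, the categorical summaries are descriptive without between-arm tests, and the primary safety objective is unaffected. Loss of response while on treatment is still captured. The full denominator is itself limited to patients who completed an originating study, so it describes treated JAIM patients and not everyone who started baricitinib. The change should be made, but the flaw does not undermine the study's main purpose.

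**What to change.** - For each binary response endpoint, add an NRI summary through Week 156 over the full endpoint-specific mITT denominator, keeping patients with an earlier discontinuation or prohibited-medication use as non-responders.
- Keep the interval version. Label its Week 156 result as applying to patients without discontinuation or prohibited medication through Week 108, print its denominator and the number excluded by arm, and footnote Table JAIM.6.4 to match.
- In 6.4.2.2, limit the statement about no missing data to patients still evaluated in the interval, and say how an on-treatment patient with a missing response is counted.
- For the SLEDAI-2K and BILAG organ-worsening rows, state which outcome NRI assigns to a patient who exits before adding the summary, since non-responder could be read as not worsened.

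The cost is one extra set of tables and a few wording changes. No new data are needed, and for the response endpoints only the denominators change. The downside is that the added Week 156 rates are lower and count every exit as non-response, whatever its reason. Keeping the interval version beside them preserves the description of patients who stay on treatment.

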### 6.4.2.3. Mixed Model for Repeated Measures

For continuous variables, an MMRM analysis with a missing at random assumption for handling missing data will be performed. This likelihood-based analysis takes into account both missingness of data and the correlation of the repeated measurements.

The MMRM method may be justified when the estimand of interest uses the hypothetical strategy (EMA2020) for handling intercurrent events. In this strategy, the scientific question of interest is to assess the effect of study treatment in a hypothetical trial where all patients have complete data and continue to take study treatment as directed without dropping out of the study.

For patients who have prohibited medication use any time after baseline, any observed data after the date of the prohibited medication use will be excluded from the MMRM analysis. The earliest date of prohibited medications will be used for censoring.

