Abbreviations: ANA = antinuclear antibody; BILAG = British Isles Lupus Assessment Group; BP = blood pressure; CLASI = Cutaneous Lupus Erythematosus Disease Area and Severity Index; C-SSRS = Columbia-Suicide Severity Rating Scale; dRVVT = Dilute Russell's Viper Venom Time; dsDNA = double-stranded deoxyribonucleic acid; EQ-5D-5L = 5-level EuroQol-5 Dimensions; ET = early termination; FACIT = Functional Assessment of Chronic Illness Therapy; HBcAb = hepatitis B core antibody; HBsAb = hepatitis B surface antibody; HBV DNA = hepatitis B virus deoxyribonucleic acid; Ig = immunoglobulin; IWRS = interactive web-response system; NRS = numerical rating scale; PGI-S = Patient's Global Impression of Severity; RNP = ribonucleoprotein; QIDS-SR16 = 16-Item Quick Inventory of Depressive Symptomatology-Self Report; SF-36v2 = Short-Form 36-item Health Survey version 2; SLE = systemic lupus erythematosus; SLEDAI-2K = Systemic Lupus Erythematosus Disease Activity Index 2000; SLICC/ACR = Systemic Lupus Erythematosus International Collaborating Clinics/American College of Rheumatology; SSA/Ro = Sjögren's-Syndrome-related antigen A; SSB/La = Sjögren syndrome type B antigen/Lupus La protein; V = visit; W = week; WPAI = Work Productivity and Activity Impairment.

- ^a Patients who discontinue from investigational product (IP) early should complete the ET visit and proceed to post-treatment follow-up.
- ^b All patients should return for Visit 801, a post-treatment follow-up visit, 28±5 days after the last dose of IP. Patients who discontinue IP but remain in the study for at least 28±5 days without IP, can combine their Visit 11/ET with their Visit 801 (post-treatment follow-up visit).
- ^c Visit 1 of Study JAIM should occur on the same day as the final visit of the originating study. Assessments/procedures required for both Visit 1 of Study JAIM and the final visit of the origination study should only be performed once.
- ^d At each time point, 3 replicate readings should be made at approximately 30- to 60-second intervals. Blood pressure is recorded as the average of these 3 readings. A single pulse measurement should be made simultaneously with at least 1 of the readings at each time point (Section 9.4.1. for details on vital signs).
- ^e Adverse events that are ongoing at the completion of the originating trial should be reported as pre-existing conditions at Visit 1 for Study JAIM.

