### 6.3. Definition of Baseline and Postbaseline Periods

For efficacy analyses, *baseline* for patients receiving active treatment (baricitinib 2-mg and 4-mg) in originating studies (JAHZ and JAIA) is defined as the last nonmissing measurement taken in the originating studies, prior to starting study medication. *Baseline* for patients receiving placebo in originating studies is defined as the last nonmissing assessment prior to the first dose of active study drug given in Study JAIM Visit 1 (Week 0). Any assessment collected after the JAIM Visit 1 dose through the date of Visit 11 or the early discontinuation visit is defined as *postbaseline* for the Treatment Period.

Protocol-defined visit windows are defined as  $\pm 4$  days for Visit 2 (Week 4),  $\pm 7$  days for Visit 3 (Week 12),  $\pm 10$  days from Visit 4 (Week 24) until Visit 7 (Week 60), and  $\pm 14$  days from Visit 8 (Week 84) until Visit 11 (Week 156). If there are data within the protocol-defined window, those data will be used in by-visit analyses. If a protocol-defined visit is missing, then the nearest unscheduled visit data that exist will be mapped to that visit and included in by-visit analyses.

For safety analyses, baseline is defined as the last nonmissing scheduled (planned) measurement prior to the first dose of baricitinib administration in Study JAIM for continuous measures by-

visit analyses and all nonmissing measurements prior to the first dose of the study drug administration (baricitinib) in Study JAIM for all other analyses.

Postbaseline measures for the safety analyses are defined as the nonmissing scheduled (planned) measurements after the first dose of baricitinib administration in Study JAIM for continuous measures by-visit analyses and all nonmissing measurements after the first dose of the study drug administration (baricitinib) in Study JAIM for all other analyses.

In general, when the baseline measurement is collected on the same day (where time is not collected) as the first dose date, this measurement will be used as the baseline value for efficacy and safety except adverse events (AEs).

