### 6.4.2.4. Modified Last Observation Carried Forward (mLOCF)

For patients who receive prohibited medication, the last nonmissing observation at or before prohibited use will be carried forward to that particular visit interval but not for the subsequent visit intervals (as defined in Section 6.4.2). For all other patients discontinuing from the study or permanently discontinuing the study treatment for any reason, the last nonmissing postbaseline observation on or before discontinuation will be carried forward to that particular visit interval but not for the subsequent visit intervals (as defined in Section 6.4.2). If a patient does not have a nonmissing observed record (or one imputed by other means) for a postbaseline visit, the last postbaseline record prior to the missed visit will be used for this postbaseline visit. If a patient does not have any postbaseline record at a scheduled, unscheduled or early termination visit, they will be excluded from the analysis.

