A by-patient listing of all concomitant medications will be provided for the mITT patients.

For corticosteroids, all doses of steroids will be converted to an equivalent dose of prednisone (see Section 6.10.1). Using the prednisone-equivalent dose, a daily dose of corticosteroid will be derived for each study day from baseline to the treatment discontinuation day for patients who discontinue treatment early or to the day before for treatment completers.

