### **6.10.1. Corticosteroid Dosing Conversion**

To allow for assessments of changes in doses of various corticosteroids, all corticosteroid doses will be standardized to an equivalent prednisone dose. [Appendix 1](#) provides a complete summary of conversion factors for each corticosteroid medication identified during the study, instructions for selecting corticosteroids, and the manual review process. An intramuscular (IM) injection is considered a single dose on the date IM injection is administered. This dose of corticosteroid will be referred to as “prednisone (or equivalent)” throughout this document.

Baseline prednisone (or equivalent) dose will be the total daily dose of all corticosteroids being taken by a patient on the day prior to the date of the first dose of study drug administration (baricitinib). This baseline dose will be used for baseline summaries and for comparisons to later visits. A daily dose of prednisone (or equivalent) will be calculated for each day between baseline and study discontinuation. The corticosteroid dose for a postbaseline visit will be the daily dose of prednisone (or equivalent) at each visit date minus 1.

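### The MMRM targets continued treatment but has no rule for permanent discontinuation, so a limited set of off-drug values can enter the LS means, and the prednisone series has two different end dates

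*SAP*

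**What the plan says.** **Target.** SAP 6.4.2.3 links the MMRM to the hypothetical strategy: the question is what would happen if patients had complete data and would "continue to take study treatment as directed without dropping out of the study".

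**Data removed.** The same section has one exclusion: "For patients who have prohibited medication use any time after baseline, any observed data after the date of the prohibited medication use will be excluded". It does not mention permanent discontinuation of study drug. NRI (SAP 6.4.2.2) and mLOCF (SAP 6.4.2.4) both name that event; under mLOCF "the last nonmissing postbaseline observation on or before discontinuation will be carried forward".

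**Efficacy window.** SAP 6.3 defines Treatment Period postbaseline data as "Any assessment collected after the JAIM Visit 1 dose through the date of Visit 11 or the early discontinuation visit". It does not say whether that last visit marks leaving treatment or leaving the study.

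**Visit path after stopping.** Footnote a of the protocol's Schedule of Activities (Section 2) sends patients who stop drug early to the ET visit and then to follow-up. Footnote b adds an exception: "Patients who discontinue IP but remain in the study for at least 28±5 days without IP, can combine their Visit 11/ET with their Visit 801". The schedule sets no day limit for ET. Protocol 8.1.3 lets some inadvertently enrolled patients stay in the study without study drug.

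**Temporary interruption.** SAP 6.4 keeps measurements taken while drug is suspended.

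**Prednisone dose.** SAP 6.10 runs the daily series "from baseline to the treatment discontinuation day for patients who discontinue treatment early". SAP 6.10.1 says: "A daily dose of prednisone (or equivalent) will be calculated for each day between baseline and study discontinuation".

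**The concern.** SAP Section 4 points to 6.4.2 for the handling of intercurrent events. Stopping study drug for good is the event that most directly breaks a hypothetical of continued treatment, and the MMRM section is silent on it. Under the stated target and the missing-at-random assumption, a value recorded weeks after the last dose should be treated as missing. Read literally, the SAP keeps it whenever it falls inside the 6.3 window and no prohibited drug has been started.

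What is at stake is the meaning of the within-arm LS means, intervals and p-values. Table JAIM.6.4 assigns MMRM to every continuous efficacy and health-outcome endpoint except SLICC/ACR, with Week 156 as the key time point. If some of those values are off drug, the estimates describe neither continued treatment nor a clean treatment-policy question. For prednisone dose, two programmers following two adjacent sections could build different datasets.

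**Working it through.** The plan gives no figure that depends on this rule, so there is none to reproduce. The check sets the rules side by side, traces which values can pass, and then sizes the effect on assumed inputs.

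**Step 1. Which off-drug values pass the written rules?**

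| Value | Inside the SAP 6.3 window? | Removed by SAP 6.4.2.3? |
|---|---|---|
| Separate Visit 801 after ET | No | Not needed |
| ET shortly after the last dose | Yes | No, but reflects state at stopping |
| ET well after the last dose | Yes | No |
| Visit 11/ET combined with Visit 801 | Yes | No |
| Visits of patients kept without drug (protocol 8.1.3) | Yes, up to Visit 11 or early discontinuation | No |
| Visits during temporary interruption | Yes | No; kept on purpose by SAP 6.4 |

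The interval rule in SAP 6.4.2 does not close the gap. It is keyed to leaving the study, and its intervals are defined for NRI and mLOCF.

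**Step 2. How certain is entry into the model?** A combined Visit 11 held within Day 1093 ± 14 is a Week 156 value under SAP 6.3 and enters directly. For an ET value, 6.3 gives no explicit visit assignment; it describes only in-window data and the mapping of the nearest unscheduled visit. Entry by that route is possible, not certain.

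**Step 3. Minimum time off drug at a combined visit.** Footnote b gives 28 ± 5 days, so 28 − 5 = 23 days.

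**Step 4. Size, on assumed inputs.** The documents give neither the share *f* of off-drug values at a visit, nor their mean difference *d* from on-drug values, nor the within-patient correlation ρ. Assume *f* = 1% to 10%, *d* = 0.25 to 1.0 SD and ρ = 0.5 to 0.7.

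- Direct shift of a visit mean = *f* × *d*. Lowest: 0.01 × 0.25 = 0.0025, about 0.003 SD. Highest: 0.10 × 1.0 = 0.10 SD. At *d* = 0.5 SD, *f* = 1%, 5% and 10% give 0.005, 0.025 and 0.05 SD.
- Carry-over: if an off-drug ET value enters at one visit and later visits are missing, the likelihood fit moves the later mean by ρ × *f* × *d*. With *d* = 0.5 SD and *f* = 2% to 10%, ρ = 0.5 gives 0.005 to 0.025 SD and ρ = 0.7 gives 0.007 to 0.035 SD. A two-visit maximum-likelihood simulation agreed with this formula to within 0.001 SD (for example, 0.0353 against 0.035).

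**Step 5. Prednisone.** SAP 6.10.1 takes the visit dose from the day before the visit. Suppose treatment is discontinued on day D and a combined visit falls on day D + 23. The dose needed is that of day D + 22. Under 6.10 the series ended on day D, so there is no value. Under 6.10.1 the series runs to study discontinuation, so there is one. This conflict needs no assumption.

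**The case against.** The strongest reply is that prohibited medication is not the only cut. SAP 6.3 closes the efficacy window at Visit 11 or the early discontinuation visit, and the protocol does not keep patients who stop drug on the remaining visits. A reader might infer from 6.4.2.3 alone that post-discontinuation data enter the model generally; the documents do not support that. Nor do they support an off-drug interval as long as the 24 weeks (168 days) between visits after Week 60 as part of the plan. Such a patient would have to miss both ET and the Visit 801 due 28 ± 5 days after the last dose.

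A reader might also infer that the shift runs against the drug and differs by arm. The documents give no off-drug course, no share of combined visits and no discontinuation rate by arm, so direction and imbalance are unknown. The mLOCF contrast should not be pressed either: Table JAIM.6.4 uses mLOCF only for SLICC/ACR, so no single endpoint receives both cuts. It shows only that the SAP treats treatment discontinuation as an event elsewhere.

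Finally, these are secondary endpoints in a safety study, SAP 6.1 plans no between-arm inference unless otherwise stated, and 6.4.2.3 says only that MMRM may be justified under the hypothetical strategy.

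All of this limits the scope and the consequence. It does not supply the missing rule, does not deal with footnote b at Week 156, and does not reconcile 6.10 with 6.10.1.

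**Conclusion.** The point holds in limited form. The stated estimand and the MMRM data rule do not match, because permanent discontinuation has no exclusion. The values affected are combined Visit 11/ET/801 assessments, late ET assessments and the visits of patients retained without drug. The size cannot be derived from the documents. On the assumed shares and differences it is 0.003 to 0.10 SD for a visit mean, so probably small, and it bears only on the interpretation of within-arm secondary estimates. The two prednisone end dates are a plain contradiction whatever those assumptions. Both deserve correction; neither touches the primary safety objective.

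**What to change.** 1. In SAP 6.4.2.3, exclude efficacy values collected after permanent discontinuation of study drug, except an ET assessment made promptly after the last dose. State that window in days. A strict cut at discontinuation would discard prompt ET values, which record the patient's state at stopping and which the missing-at-random analysis needs.
2. In SAP 6.3, classify any Visit 11/ET combined with Visit 801 as follow-up for efficacy.
3. End the daily prednisone series at treatment discontinuation in both 6.10 and 6.10.1.
4. Reword the estimand in 6.4.2.3 to say that values during temporary interruption are kept, as SAP 6.4 already states.

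Leave Table JAIM.6.5 unchanged: it defines the safety period, and its by-visit analyses already exclude the follow-up visit.

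The cost is SAP wording and a date filter on data already collected. The downside is a few fewer late observations and slightly wider intervals.
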